7.2.2.6.1 Hematology

Hematology tests are to be performed according to the visit schedule outlined in Table 7-1. For details of the Hematology panel see Table 7-5.

Hematology should be assessed on the actual scheduled day, even if study drug is being withheld.

7.2.2.6.2 Clinical chemistry

Biochemistry tests are to be performed according to the visit schedule outlined in Table 7-1. For details of the Biochemistry panel see Table 7-5. Biochemistry should be assessed on the actual scheduled day, even if study drug is being withheld. Estimate of GFR (via estimated creatinine clearance rate) will be done centrally using the Cockcroft-Gault formula.

Estimated creatinine clearance rate (eCcr) using Cockcroft-Gault formula

 $eC_{Cr} = rac{(140 - {
m Age}) \, imes \, {
m Mass} \, ({
m in \, kilograms}) \, imes \, [0.85 \, if \, Female]}{72 \, imes \, {
m Serum \, Creatinine} \, ({
m in \, mg/dL})}$

When serum creatinine is measured in µmol/L:

 $eC_{Cr} = rac{(140 - \mathrm{Age}) \, imes \, \mathrm{Mass} \, (\mathrm{in \, kilograms}) \, imes \, Constant}{\mathrm{Serum \, Creatinine} \, (\mathrm{in \, \mu mol/L})}$

Where Constant is 1.23 for men and 1.04 for women.

7.2.2.6.3 High-sensitivity C-reactive protein (hs-CRP) and High-sensitivity Interleukin-6 (hs-IL-6)

This marker of inflammation will be monitored according to the visit schedule outlined in Table 7-1 and Table 7-5. Sample handling and shipping instructions will be provided in the Laboratory Manual. Results for hs-CRP and hs-IL-6 will not be communicated to the investigative sites during study conduct and will remain blinded until the time of database lock.

7.2.2.6.4 Coagulation

7.2.2.6.5 INR and aPTT are to be performed according to the visit schedule outlined in Table 7-1. Urinalysis

Urinalysis is to be performed according to the visit schedules outlined in Table 7-1. For details of the urinalysis panel see Table 7-5.

7.2.2.6.6 Pregnancy and assessments of fertility

During screening, a serum pregnancy test will be completed (Day -28 to Day -1). On Cycle 1 Day 1 prior to dosing and at subsequent cycles, a urinary pregnancy test (dipstick) will be performed. A serum pregnancy test will also be completed at EOT. The time windows granted for pregnancy testing are identical to the corresponding visit time windows for each visit. Refer to Table 7-1. If local requirements dictate otherwise, local regulations should be followed.

As per Section 2.7, during a public health emergency as declared by local or regional authorities i.e. pandemic, epidemic or natural disaster, that limits or prevents on-site study visits, if participants cannot visit the site to have serum pregnancy tests, urine pregnancy test kits may be used. Relevant subjects can perform the urine pregnancy test at home and report the result to the site. It is important that participants are instructed to perform the urine pregnancy test first and only if the test result is negative proceed with the administration of the study treatment. A communication process should be established with the subject so that the Site is informed and can verify the pregnancy test results (e.g., following country specific measures).

Women who are determined not to be of child bearing potential before the study will only be tested at screening. When non-child bearing potential status is determined during the study, further pregnancy testing will not be continued. Women are considered post-menopausal if they have had 12 months of natural (spontaneous) amenorrhea with an appropriate clinical profile (e.g. age appropriate, history of vasomotor symptoms), and otherwise not of child bearing potential if they have had surgical bilateral oophorectomy (with or without hysterectomy), total hysterectomy, or bilateral tubal ligation at least six weeks prior to first dose of study drug. In the case of oophorectomy alone, only when the reproductive status of the woman has been confirmed by follow up hormone level assessment is she considered not of child bearing potential (such testing is not covered as part of the study assessments). If local requirements dictate otherwise, local regulations should be followed.

If a positive pregnancy test is performed in between study visits, the subject must immediately notify the investigator.

7.2.2.7 **Cardiac assessments**

7.2.2.7.1 Electrocardiogram (ECG)

Local single 12-lead ECGs should be recorded after the subject has been resting for 5-10 min prior to the timepoint indicated in Table 7-1.

An unscheduled ECG may be repeated at the discretion of the investigator at any time during the study and as clinically indicated. Interpretation of the tracing must be made by a qualified physician and documented in the appropriate eCRF.

Each ECG tracing should be labeled with the study number, subject initials (where regulations permit), subject number, date, and kept in the source documents at the study site. Clinically significant ECG abnormalities present at screening should be reported on the appropriate eCRF. New or worsened clinically significant findings occurring after informed consent must be recorded on the appropriate eCRF.

7.2.3 Pharmacokinetics, immunogenicity and pharmacodynamics

7.2.3.1 Pharmacokinetic, immunogenicity and pharmacodynamics blood collection and handling

Time points of blood sample collection for canakinumab PK, IG and PD are outlined in Table 7-6. If a subject starts new antineoplastic therapy after discontinuing study treatment, no further PK/PD/IG samples need to be collected. Blood samples will be taken by either direct venipuncture or an indwelling cannula inserted in a forearm vein.

For each scheduled PK sample, 2.5 mL of blood will be collected into SST tubes. The blood sample will be allowed to clot over a minimum of 30 minutes at room temperature prior to harvesting of the serum. The serum will be obtained by centrifugation at approximately 2500 g for 10 minutes. Serum PK samples will be split into 2 aliquots of approximately 0.5 mL serum (polypropylene tubes) and then stored (within 30 min of preparation) at -24°C (approximately) prior to shipment to the Sponsor or central lab (see sample storage information below for detailed stability information). One aliquot will be shipped on dry ice to the analytical laboratory. The remaining aliquot must be kept at the central lab as a backup sample. Remaining samples will only be disposed of after approval by Novartis.

For each scheduled IG sample, 2.5 mL of blood will be collected into SST tubes. The blood sample will be allowed to clot over a minimum of 30 minutes at room temperature prior to harvesting of the serum. The serum will be obtained by centrifugation at approximately 2500 g for 10 minutes. Serum IG samples will be split into 3 aliquots of approximately 0.3 mL serum (polypropylene tubes) and then stored (within 30 min of preparation) at -70°C (approximately) prior to shipment to the Sponsor or central lab (see sample storage information below for detailed stability information). Two aliquots will be shipped on dry ice to the analytical laboratory. The remaining aliquot must be kept at the central lab as a backup sample. Remaining samples will only be disposed of after approval by Novartis. If anaphylactoid reactions occur after injection, two more samples (at the time of the event and 8 weeks later) need to be taken.

For each scheduled PD (IL-1 β) sample, 3.5 mL of blood will be drawn into SST tubes, to obtain 1.5 mL serum. The sample will be allowed to clot during 45 minutes at room temperature. The serum will be obtained by centrifugation at approximately 2500 g for 10 minutes. The sample will be split into two aliquots of 0.7 mL to be transferred into freezer-proof polypropylene screw-cap tubes. Serum tubes will be frozen within 90 min of venipuncture and kept at -24°C pending shipment on dry ice. One aliquot will be shipped on dry ice to the analytical laboratory. The remaining aliquot must be kept at the central lab as a backup sample.

On days and time points where blood IG and PD samples are to be drawn, the PK sample must be drawn first. The exact collection date and time of all samples must be documented on the PK, IG and PD blood collection eCRF pages. The date and exact time of dosing, as well as the date and actual time of blood sampling must be recorded on the eCRF.

All samples will be given a unique sample number and a dose reference ID.

Further details on labeling of the PK, IG and PD samples, instructions for the collection, handling and shipment of samples can be found in the [CACZ885T2301 laboratory manual]. If subjects experience a SAE or an AE leading to the discontinuation of the study treatment, an unscheduled PK and IG blood sample should be obtained as close as possible to the event

occurrence. The date and time of the last dose and the time of PK and IG blood draw should be recorded.

Collection of PK, PD and/or IG samples may be stopped upon decision of the Sponsor, if/when sufficient data are collected, after the primary CSR cut-off date is reached or following decision to stop the study.

Table 7-6	Blood collection (serum) for canakinumab pharmacokinetics (PK),
	immunogenicity (IG) and pharmacodynamics (PD)

	eference ation (ID)	PK	IG	Total IL-			luled time point	points (hours)
Dose ID following sampling	Dose ID prior to sampling*	sample number	sample number ^b	1β (PD) sample number ^b	Cycle	Day	Scheduled time (hours)	Description
1	-	101	201	301	1	1	0 hr ^a	Pre-dose
-		104	-	-	1	8	168 hr (±12h)	Post-dose
1	1	105		302	1	15	336 hr (±24h)	Post-dose
2	1	106	202	-	2	1	0 hr (or 504 hr post- C1D1 dose)	Pre-dose
3	400	107	203	303	4	1	0 hr	Pre-dose
4	401	108	204		6	1	0 hr	Pre-dose
5	402	111	205	T	9	1	0 hr	Pre-dose
6	403	112	206	304	12	1	0 hr	Pre-dose
10	2	115	209	306	18/EOT**	NA	Anytime	Pre/Post-dose**
-	2	116	210	307	safety follow-up 1	NA	Anytime	-
-	-	117	-	-	safety follow-up 2	NA	Anytime	-
-	3	118	211	308	safety follow-up 3	NA	Anytime	-
-	2	119	-	i.	safety follow-up 4	NA	Anytime	-
-	-	120	212	309	safety follow-up 5	NA	Anytime	-
NA	NA	1001+ ^c	2001+ ^d	3001+ ^e	NA	NA	Unscheduled and at the time of progression or AE	-

	eference ation (ID)	РК	IG Total IL-	×к IG		Scheo	luled time poin	ts (hours)
Dose ID following sampling	Dose ID prior to sampling*	sample number	sample number ^t	1β (PD) sample number ^b	Cycle	Day	Scheduled time (hours)	Description
* These dose reference IDs refer to the dose administered and dosing time of the last dose prior to collection of								

the corresponding PK, IG and PD sample. ** This collection is mandatory for all subjects that end or complete study treatment. If the subject completes

treatment, this sample will be collected pre dose for cycle 18. If the subject presents for EOT visit as a result of discontinuation, then this will be a post-dose collection relative to the last dose administered.

^a Sample should be taken immediately prior to the next administration of canakinumab.

^b IG and PD samples are to be collected together with PK samples at the same time.

° PK sample numbers for any unscheduled PK collection will start with 1001.

^d IG sample numbers for any unscheduled IG collection will start with 2001.

^e PD sample numbers for any unscheduled PD collection will start with 3001.

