6.3 Dose modifications

6.3.1 Dose modification and dose delay

For subjects who do not tolerate the protocol-specified dosing schedule, dose interruptions are either recommended or mandated in order to allow subjects to continue the study treatment. **There are no dose reductions allowed in this study.**

These dose modifications are summarized in Table 6-2. If mandatory dose interruptions are not performed, deviations will be noted. Permanent treatment discontinuation is mandatory for specific events indicated as such in Table 6-2 or listed in Section 7.1.4.

Scheduled dosing of study drug may, at the discretion of the Investigator, be delayed by up to 7 days if subjects present with conditions that require withholding of study drug, e.g., presence of skin ulcer or evidence for active infection (treated or untreated). Outside of this 7 day window, the dose will be considered missed. After a dose is missed, the subject should resume treatment on the original schedule of study drug administration per C1D1. If a subject requires a dose interruption of greater than 42 days from the intended day of the next scheduled dose,

then the subject must be discontinued from the study. Subjects who discontinue the study for a study related adverse event or an abnormal laboratory value must be followed as described in Section 7.1.4.

Infections

Infections are the most common adverse event and may be related to study medication. Subjects should be followed closely for any signs or symptoms of infection and receive prompt appropriate treatment for any suspected infection. Respiratory infections are common in subjects who have had lung cancer, in part due to underlying lung diseases such as chronic obstructive pulmonary disease and other smoking or second-hand smoke related lung diseases. Subjects will have a urinalysis performed at every study visit (screening and throughout the study treatment); occult urinary tract infections, if not promptly treated may result in urosepsis. Site personnel should be aware of this concern and review urinalysis results and take action if treatment of the subject for a urinary tract infection is required.

Novartis	
Amended Protocol Version 03 (Clean)	

Table 6-2 Criteria for dose interruption and re-initiation of treatment for adverse drug reactions

Dose Schedule modifications for Canakinumab ^a	
Worst toxicity	
CTCAE Version 5.0 during a cycle of therapy	
Infections fall under many CTC terms	

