7.1.4 Discontinuation of study treatment

Subjects who discontinue study treatment should NOT automatically be considered withdrawn from the study. See Table 7-1 for the required assessments of these subjects after discontinuation of study treatment. Subjects who discontinue study treatment during the treatment phase should be scheduled for a visit within 7 days or as soon as possible after the last dose of study treatment, at which time all of the assessments listed for the EOT visit will be performed. If a subject withdraws from treatment at a study visit, EOT assessments that are already part of that scheduled study visit do not need to be repeated. The disposition page should be completed, giving the date and reason for stopping treatment.

For subjects who discontinue treatment for reasons other than documented disease recurrence, initiation of new antineoplastic therapies, death, lost to follow-up, or withdrawal of consent, assessments must continue to be performed according to Table 7-1 until disease recurrence, withdrawal of consent by the subject, subject is lost to follow up, death or the sponsor terminates the study for up to five years.

Confidential

Subjects may voluntarily discontinue from the study for any reason at any time. If a subject decides to discontinue from the study, the investigator should make a reasonable effort (e.g. telephone, e-mail, letter) to understand the primary reason for this decision and record this information in the subject's chart and on the appropriate eCRF pages. They may be considered withdrawn if they state an intention to withdraw, fail to return for visits, or become lost to follow-up for any other reason. The investigator must also contact the IRT to register the subject's discontinuation from study treatment.

At a minimum, all subjects who discontinue study treatment, including those who refuse to return for a final visit, will be contacted for safety evaluations during the 130 days following the EOT visit (see Section 7.1.6.1).

The investigator may discontinue study treatment for a given subject if, he/she believes that continuation would be detrimental to the subject's well-being.

In addition to mandatory study drug discontinuation criteria listed in Table 6-2, treatment must also be discontinued under the following circumstances:

- Pregnancy
- Study Terminated by Sponsor
- Subject/guardian decision
- Physician decision

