7.1.6 Follow up evaluations

7.1.6.1 Safety follow up

All subjects will be followed for AEs and SAEs for at least 130 days following the EOT visit. Subjects will present to the clinical site every 28 days, for a total of five follow-up visits (see Table 7-1). At the end of this period, the investigator should assess and discuss with the subject any AEs observed and concomitant medications taken since discontinuation of study treatment. Subjects whose treatment is permanently discontinued due to an AE (clinical or based on abnormal laboratory value) must be followed until resolution or stabilization of the event, whichever comes first. In case of an abnormal laboratory value, blood tests should be repeated until resolution or stabilization.

If a new antineoplastic therapy is initiated after discontinuation of study treatment, only SAEs suspected to be related to study treatment will be collected in the Adverse Events eCRF.

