2.9 Pharmacokinetic endpoints

PAS will be used in the pharmacokinetic data analysis.

PK concentrations

Descriptive statistics (n, m (number of non-zero concentrations), arithmetic mean, CV% mean, SD, median, geometric mean, CV% geo-mean, minimum and maximum) for canakinumab concentration will be presented at each scheduled time point for the PAS.

Individual concentration-time profiles for canakinumab evaluable concentrations with median will be displayed graphically for PAS on the semi-log view. In addition, the mean (+/- SD) and geometric mean concentration-time profiles for canakinumab over time will be displayed graphically for PAS on the linear and semi-log view. Only time points with $n \geq 4$ observations will be shown on the figure.

All individual plasma canakinumab concentration data will be listed by treatment for the FAS.

Handling of PK data below LLOQ or missing

All concentration values below the lower limit of quantitation (LLOQ) are set to zero by the Bioanalyst, and will be displayed in the listings as zero and flagged. LLOQ values will be treated as zero in any calculations of summary statistics, and treated as missing for the calculation of the geometric means and their CV%. The number of non-zero concentrations will also be reported in the summary statistics.

Missing values for any PK data will not be imputed and will be treated as missing.

Population pharmacokinetic analysis

If there is adequate amount of data, a mixed-effects model may be applied to the serum canakinumab concentration-time data from this study to characterize canakinumab exposure and to determine the effects of intrinsic (i.e. demographic factors) and extrinsic covariates (e.g. concomitant medications) on canakinumab exposure. If there is sufficient data for analysis, the details of the population pharmacokinetic analyses may be provided in a separate reporting and analysis plan, and the results may be reported in a separate population pharmacokinetic report.

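### Descriptive PK summaries at C18/EOT and in washout mix samples taken at different times since the last dose, because EOT timing differs between completers and early stoppers

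*Protocol*

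**What the plan says.** **Sampling.** Protocol Table 7-6 (section 7.2.3.1) has a single 18/EOT row: PK sample 115, timed Anytime and described as pre- or post-dose. Its footnote gives the row two meanings. If the subject completes "treatment, this sample will be collected pre dose for cycle 18". If the subject comes to EOT because of discontinuation, "then this will be a post-dose collection relative to the last dose administered". Table 7-1 likewise gives C18/EOT one visit number.

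**EOT timing.** Under protocol 7.1.4, subjects who discontinue during the treatment phase "should be scheduled for a visit within 7 days or as soon as possible after the last dose of study treatment". That is a target with no upper limit.

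**Follow-up.** Samples 116-120 are taken at the five safety follow-up visits, also timed Anytime. Protocol 7.1.6.1 anchors that period to EOT: "All subjects will be followed for AEs and SAEs for at least 130 days following the EOT visit". The spacing is also given there: "Subjects will present to the clinical site every 28 days, for a total of five follow-up visits".

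**Summaries.** SAP 2.9 states that descriptive statistics "for canakinumab concentration will be presented at each scheduled time point for the PAS", with mean and geometric mean profiles over time. SAP 2.2 requires pre-dose samples (other than Cycle 1 Day 1) to fall 16 to 26 days after the last 200 mg dose. A post-dose sample needs only an earlier 200 mg dose. The visit windows in SAP Tables 2-1 and 2-7 cover PRO/ECOG and laboratory data, not PK.

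**The concern.** A table by scheduled time point is readable when the label fixes the time since dosing. Here two labels do not. The C18/EOT row joins troughs after 17 doses with samples from early stoppers that may be near peak or partly washed out, after fewer doses. Each follow-up row joins completers at a known interval from dose 18 with early stoppers at that interval plus their own EOT delay.

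The last on-treatment point and the tail of the mean profiles would then reflect who stopped and when, as well as the drug's kinetics. Characterising PK is a stated secondary objective, and the population PK model, which could use actual times, is optional in both documents. The concentration-by-ADA tables (14.2-4.1a to d) are downstream of the same samples.

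**Working it through.** **Inputs from the protocol.** Half-life 26 days, V 6.01 L, CL 0.174 L/day, F 0.66, ka 0.28-0.38/day (1.3.1.2.3, from CAPS subjects); 200 mg every 21 days; LLOQ 300 ng/mL outside China (7.2.3.2). The share of early stoppers is not in the documents; I assume 10-40%.

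**The plan's own figure.** SAP 2.1.1 calls 130 days about five half-lives: 5 × 26 = 130, reproduced. As a cross-check, ln 2 × 6.01/0.174 = 23.9 days, so I also ran that half-life.

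**Time since last dose.**
- C18/EOT, completers: 16-26 days if evaluable.
- C18/EOT, early stoppers: 0-7 days if the target is met. The outer case follows from protocol 6.3.1: "If a subject requires a dose interruption of greater than 42 days from the intended day of the next scheduled dose", the subject is discontinued, so about 21 + 42 = 63 days is plausible.
- Follow-up 1: completers are dosed at C18/EOT, so day 28. Early stoppers are at 28 days plus their lag: 35, 49 or 91 days for lags of 7, 21 or 63.

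**Illustrative model.** One compartment with first-order absorption, n doses, d days after the last:

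C(n,d) = A × Σ(j=0..n−1) [exp(−k(d+21j)) − exp(−ka(d+21j))]

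With k = ln 2/26 = 0.02666 and ka = 0.33, A = 0.66 × 200 × 0.33 / (6.01 × (0.33 − 0.02666)) = 23.89 µg/mL.

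C18 trough, n = 17, d = 21: the two sums are 1.3325 and 0.0010, so 23.89 × 1.3315 = 31.8 µg/mL.

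| Sample sharing the C18/EOT label | µg/mL |
|---|---|
| 17 doses, day 21 (true trough) | 31.8 |
| 17 doses, day 7 | 43.9 |
| 17 doses, day 63 | 10.4 |
| 1 dose, day 1 | 6.1 |
| 1 dose, day 63 | 4.5 |

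**Follow-up 1.** Completer at day 28: 26.4. Near-steady-state stopper at day 49: 26.4 × 2^(−21/26) = 26.4 × 0.571 = 15.1, which is 43% lower. With a 23.9-day half-life the ratio is 2^(−21/23.9) = 0.544, or 46% lower.

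**Pooled C18/EOT mean relative to the true trough.**
- 20% stoppers, all at day 7 near steady state: (0.8 × 31.8 + 0.2 × 43.9)/31.8 = 1.08.
- 20%, all at day 63 near steady state: (0.8 × 31.8 + 0.2 × 10.4)/31.8 = 0.87.
- 40%, half in each of those groups (mean 27.15): (0.6 × 31.8 + 0.4 × 27.15)/31.8 = 0.94.
- Extremes over 10-40% stoppers and all parameter values: 0.65 to 1.18. The low end puts all 40% at one dose and day 63.

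**Pooled follow-up 1 mean, stoppers at day 49.** 20%: 0.8 × 26.4 + 0.2 × 15.1 = 24.1, 9% below completers. 40%: 0.6 × 26.4 + 0.4 × 15.1 = 21.9, 17% below.

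**Late follow-up.** At follow-up 5 completers are at about 0.9-1.4 µg/mL. A stopper with a 63-day lag after 12 doses is at about 0.25 or lower, under the 0.3 µg/mL LLOQ. SAP 2.9 counts such values as zero in arithmetic means and drops them from geometric means, so the two curves can separate for reasons unrelated to kinetics.

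**The case against.** **The SAP does not say in words that the two kinds of sample are pooled.** Table 7-6 marks the row as pre/post-dose, SAP 2.2 treats the two types under different rules, and the primary table shells are not in the documents. A split table would be compatible with the text. This stands in part: the defect is a missing rule. But one row, one sample number and a summary by scheduled time point lead to pooling unless someone decides otherwise.

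**The spread is driven by extreme cases.** This also stands in part. EOT is targeted within 7 days. A stopper seen at day 21 has a trough-like value at C18/EOT: after five doses accumulation is 1 − 2^(−5×21/26) = 94% of steady state. That same subject is nevertheless at day 49 at follow-up 1. Protocol 7.2.3.1 also waives further PK samples once new antineoplastic therapy starts, which thins early stoppers in the follow-up rows.

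**Stronger readings that a reader might infer, and that the documents do not support:**
- *Trough or exposure-response results are contaminated.* Protocol 10.5.4 and SAP 2.10.1.1 restrict Ctrough to pre-dose samples, and the steady-state version to evaluable ones from Cycle 6. Early EOT and follow-up samples do not enter.
- *The means relate to no defined time at all.* Completers do have defined times: 16-26 days at C18 and nominally 28 × k days at follow-up k. Only the early-stopper admixture is undefined.
- *Total IL-1β has the same fault.* The protocol summary mentions a summary by time point, but the visible SAP has no rule for it and nearby text is blacked out.
- *The ADA tables are materially distorted.* No effect has been quantified, and the ADA incidence of 0.5-2.9% in protocol 1.3.1.2.3 means sparse positive cells in any case.

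**Conclusion.** The point holds as a minor one, confined to descriptive PK. Followed as written, the plan mixes times since dose in the C18/EOT statistics and in the washout part of the mean profiles. The clearest effect is at follow-up: about 26 against 15 µg/mL for two subjects under one label, and a pooled follow-up 1 mean 9-17% below completers if 20-40% of subjects are early stoppers at day 49. The C18/EOT mean may move only modestly, in either direction, because early and late samples partly cancel; the spread is affected more than the centre.

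The concentrations rest on a one-compartment model with CAPS parameters, and the pooled shifts on an assumed stopper share and timing. The mixing itself rests on neither. Trough, exposure-response and DFS/OS analyses are untouched. Individual profiles and the full listing in SAP 2.9 remain available to a careful reader.

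**What to change.** In SAP 2.9:

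1. Summarise Cycle 18 pre-dose as its own time point, under the existing 16-26 day evaluability rule.
2. Report early-discontinuation EOT samples separately, with days since last dose and number of doses received.
3. Tabulate and plot samples 116-120 by actual days since last dose. This also avoids choosing between the protocol's 28-day visit spacing and the 26-day spacing in SAP Tables 2-1 and 2-7, neither of which is set out for PK.
4. Carry the same labels into the concentration-by-ADA tables, which use the same samples.

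The cost is SAP wording and programming. Protocol 7.2.3.1 already requires exact dose and sample dates and times in the eCRF, so no new data are needed.
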